6.2.6 Week 26 Visit

The Week 26 Visit is the last visit of the Long-Term Treatment Phase. This visit is performed approximately 6 months after the Baseline Visit (Day 1) and the next day following administration of the last dose of patiromer.

The activities for Week 26 (\pm 7 days) are detailed below and Appendix B:

- Subject's visit registration in IWRS
- Physical examination
- Body weight and height
- Vital Signs (resting heart rate and sitting BP)
- 12-Lead ECG
- Potassium levels (measured locally and by central laboratory)
- Other central laboratory tests (see Appendix C):
 - Serum chemistry
 - Plasma parathyroid hormone
 - Serum fluoride
 - Urinalysis (not required for anuric subjects, see section 7.2)

- Hematology (CBC)
- Urine pregnancy test (female subjects of child-bearing potential only; measured locally and by central laboratory). In the event of a positive or equivocal urine pregnancy test result or if the subject is anuric, a serum Pregnancy test will be performed.
- Patiromer reconciliation, accountability and compliance
- Assessment of AEs
- Assessment of concomitant medications
- Next visit scheduling

6.3 Follow-up Period

Subjects who complete the Long-Term Treatment Phase will enter the 2-week Follow-up Period thereafter. Subjects who discontinue treatment with patiromer early during either the 14-day PD / Dose Finding Phase or Long-Term Treatment Phase enter directly into the Follow-up Period. The Follow-up Period consists of one visit (Follow-up Visit 1) at 1 week after the last patiromer treatment and one phone call (Follow-up Visit 2) at 2 weeks after the last patiromer treatment. Follow-up Visit 2 may be converted into an onsite visit at the investigator's discretion if potassium level from Follow-up Visit 1 is of concern.

6.3.1 Follow-up Visit 1 (F1)

Subjects must return for the F1 Visit 7 days (\pm 3 days) after stopping patiromer treatment (see Section 6.3 and Appendix B).

The following activities will be performed:

- Subject's visit registration in IWRS
- Vital Signs (resting heart rate and sitting BP)
- 12-Lead ECG (Only if local K⁺ is > 6.0 mEq)
- Potassium levels (measured locally and by central laboratory)
- Serum chemistry (see Appendix C)
- Assessment of AEs
- Assessment of concomitant medications
- Next phone call scheduling

6.3.2 Follow-up Visit 2 (F2)

Follow-up Visit 2 is a phone call to the subject's parent or legal guardian 14 days (\pm 3 days) after stopping patiromer treatment (see Section 6.3 and Appendix B). If subjects are requested to return for an onsite visit, the same activities will be performed as those listed in Section 6.3.1.

The following activities will be performed based on the phone call:

- Subject's visit registration in IWRS
- Assessment of AEs
- Assessment of concomitant medications

6.4 Early Termination Visit

Subjects who withdraw prematurely from the study before the Week 26 Visit will need to complete the ET Visit, which should be performed on the day of withdrawal or as soon as possible after the last dose of patiomer. Subjects who prematurely stop study drug should be encouraged to complete the Follow-up Period Visits (Section 6.3, Appendix A and Appendix B).

The following activities will be performed:

- Subject's visit registration in IWRS
- Physical examination
- Body weight and height
- Vital Signs (resting heart rate and sitting BP)
- 12-Lead ECG
- Potassium levels (measured locally and by central laboratory).
- Other central laboratory tests (see Appendix C):
 - Serum chemistry
 - Plasma parathyroid hormone
 - Serum fluoride
 - Urinalysis (not required for anuric subjects, see section 7.2)
 - Hematology (CBC)
- Urine pregnancy test (women of child-bearing potential only; measured locally and by central laboratory). In the event of a positive or equivocal urine pregnancy test result or if the subject is anuric, a serum Pregnancy test will be performed
- Follow-up visit scheduling
- Patiomer reconciliation, accountability, compliance
- Assessment of AEs
- Assessment of concomitant medications

6.5 Other Visits

6.5.1 Safety Visit

Safety Visits are mandatory in certain situations. Mandatory Safety Visits are required within 7 days if subject meets any of the following criteria:

- Local potassium is > 6.0 mEq/L. If the patiromer dose is already at the maximum dose (or anticipated highest dose) for the age group, standard of care for hyperkalemia should be applied including RAASi dose decrease
- Any increase in patiromer dose that is initiated and the next scheduled study visit is > 1 week after the dose increase has been initiated
- Discontinuation per the Investigator's discretion

Note: During the 14-Day PD/Dose finding phase when local potassium measurements > 6.0 mEq/L, the Mandatory Safety Visit is not required if a standard study visit takes place within 3 days, however all listed MSV study procedures must be completed (i.e. ECG) at the standard study visit.

Treatment of these subjects with emergency care for hyperkalemia or prohibited standard of care medications (i.e., sodium polystyrene sulfonate or calcium polystyrene sulfonate) may result in the subject being removed from the study; see Section 5.6 for a complete list of prohibited medications. Investigator must contact the medical monitor to determine if the subject should continue in the study.

The following activities will occur during a Mandatory Safety Visit:

- Subject's visit registration in IWRS
- Vital Signs (resting heart rate and sitting BP)
- 12-Lead ECG if the current or most recent local potassium is > 6.0 mEq/L
- Potassium levels (measured locally and by central laboratory)
- Patiromer dose titration (if needed), dispensation, reconciliation, accountability, compliance, and subject retraining (as applicable)
- Assessment of AEs
- Assessment of concomitant medications
- Next visit scheduling

An unscheduled visit may occur at the discretion of the Investigator. At an unscheduled visit during any phase of the study, the following activities will be performed:

- Subject's visit registration in IWRS
- Assessment of AEs
- Assessment of concomitant medications

Other study procedures described in the protocol including the assessment of potassium levels (measured locally and by central laboratory) may be conducted at the discretion of the Investigator depending upon the reason for the visit.

7 ASSESSMENTS

7.1 Potassium

Eligible subjects must have K⁺ levels of 5.1 – < 6.5 mEq/L determined by two blood or serum potassium measurements performed on separate days. A standard of care potassium value measured within 42 days to 2 days prior to Screening may be used for one of the potassium values to assess eligibility. Subject's eligibility will be assessed during a Screening Period with up to two visits (Screening Visit 1, Screening Visit 2).

The following scenarios are allowed for obtaining the two qualifying potassium values (5.1 to < 6.5 mEq/L):

- For subjects **with a recent standard of care potassium measurement**, the two qualifying potassium values will be the most recent standard of care potassium measurement obtained from 42 days to 2 days prior to Screening Visit 1 and the local potassium measurement at Screening Visit 1
- For subjects **without a recent qualifying standard of care potassium measurement** within 42 days to 2 days prior to Screening Visit 1, the first qualifying potassium values will be obtained at Screening Visit 1 and the second at Screening Visit 2, occurring 2 to 7 days after Screening Visit 1

Blood and/or serum potassium levels will be assessed at every study visit (with the exception of Follow-up Visit 2, which is a phone call) and measured both locally and by central laboratory. Serum samples will be used for central laboratory potassium measurements. For Follow-up Visit 2, if the subject is requested to return for an onsite visit, then blood/serum potassium levels will be assessed (see Section 6.3.2 for details).

7.1.1 *Preventing, Identifying and Handling Hemolyzed Samples*

Hemolysis of blood specimens may result in spuriously high potassium levels, leading to inappropriate up-titrating of the investigational product and causing difficulties in interpreting the efficacy analyses.

The Laboratory Manual provides detailed descriptions of the recommended phlebotomy, sample preparation and transportation procedures to minimize hemolysis.

Upon receipt of each blood sample for potassium analysis, the central laboratory will perform a semi-quantitative test to assess for evidence of hemolysis. Pre-defined criteria have been established for determining whether the test result is indicative of potential hemolysis. These criteria and the criteria for removing serum potassium value from the efficacy analyses on the basis of hemolysis are described in the Laboratory Manual. When a central laboratory sample has been identified as hemolyzed after it has been received and processed by the central laboratory, the blood draw will not be repeated by the site personnel. The statistical analysis plan (SAP) summarizes how the data analyses will account for the missing central laboratory potassium value. If the central laboratory blood sample has been identified as hemolyzed by the site personnel before it has been sent to the central laboratory, a repeat blood draw can be performed if the subject is still at the site.

When a blood sample, which is used by the site for titration and subject management, has hemolyzed (e.g., by visual inspection of the central laboratory serum sample), the site will need to repeat the potassium measurement from a separate blood draw in order to ensure accurate decision-making regarding patiromer titration.

7.1.2 Early Withdrawal from the Study due to Potassium Levels

Study withdrawal based on potassium level is at the discretion of the Investigator, except in the situations described in Section 6.5.1. The Investigator should perform a confirmatory local potassium level before initiating subject withdrawal. Aside from adjustment of diet or adjustment of concomitant medications (e.g., RAASi dose decrease or discontinuation in the Long-Term Treatment Phase), a potassium level that requires treatment with additional medications may be a reason for ET. If a subject is early terminated because of high or low potassium, the Investigator will provide the appropriate medical management for high or low potassium according to standard of care practices.

7.2 Laboratory Tests

AST, ALT and creatinine levels will be analyzed at the local laboratory at the Screening Visit(s) to assure eligibility for the study. Magnesium level will also be analyzed at the local laboratory at the Screening Visit(s). At other time points, the AST, ALT, magnesium and creatinine levels will be analyzed by the central laboratory as per Appendix A and Appendix B. Additional tests included in the chemistry panel (Appendix C) will be analyzed by the central laboratory at time points included in Appendix A and Appendix B. For subjects that have one dose of phosphate binder replaced by patiromer, calcium and/or phosphate levels may be tested by the central laboratory more frequently per Investigator's decision.

To qualify for study entry, the subject must have an eGFR < 90 mL/min/1.73m² at screening based on local measurements. Either the Original or Bedside Schwartz formula should be used to calculate eGFR based upon the current serum creatinine assay methodology being used at the investigative site's local clinical laboratory.

- The Bedside Schwartz formula [$eGFR = 0.413 \times [\text{height (cm)}/\text{serum creatinine (mg/dL)}]$] (Schwartz, 2009) requires enzymatic creatinine assay, which may not be available at all institutions. In cases where the study site's local laboratory uses the Jaffe creatinine assay that is isotope dilution mass spectrometry (IDMS) traceable, then the Bedside Schwartz formula should be used to calculate eGFR
- In clinical laboratories that use the Jaffe method for creatinine determination that is not isotope dilution mass spectrometry (IDMS) traceable, eGFR should be calculated using the Original Schwartz formula [$eGFR = k \times [\text{height (cm)}/\text{serum creatinine (mg/dL)}]$, where the value for k is 0.45 for term infants through the first year of life, 0.55 for children and adolescent girls and 0.7 for adolescent boys] (Schwartz, 2009)

Hematology (CBC including WBC, RBC, hemoglobin, hematocrit, and platelet count) will be analyzed by the local laboratory at the Screening Visit(s) to assure eligibility for the study. At other

time points, the hematology panel (Appendix C) will be assessed by central laboratory as per Appendix A and Appendix B.

For female subjects of child bearing potential only, a urine pregnancy test will be assessed locally and a serum pregnancy test will be performed by the central laboratory. For anuric female subjects of child bearing potential, a serum pregnancy test will be assessed locally and by the central laboratory. Anuric female subjects of child bearing potential cannot be enrolled into the study until a local negative serum pregnancy test is demonstrated.

Urinalysis (see Appendix C) will be assessed by central laboratory. Urinalysis will not be required for anuric subjects.

7.3 Vital Signs

7.3.1 Heart Rate

In children over 2 years of age, heart rate can accurately be assessed by measuring the pulse radially in most children. In the event peripheral pulses are difficult to palpate, heart rate may be assessed by auscultation of the apical pulse for one full minute. The apical pulse is assessed over the point of maximum impulse (PMI) on the child's chest. In children up to 7 years old, the PMI is usually found at the 4th rib interspace medial to the nipple (the midclavicular line). After Age 7 - 8, the PMI is found between the 5th and 6th interspace, as it is in the adult.

Heart rate should be measured prior to BP measurement, and should be measured for a full 60 seconds. Heart rate data for each visit should be recorded in the respective eCRF.

7.3.2 Blood Pressure

When taking BP measurements, Investigators shall follow the following recommendations:

- Throughout the study, BP measurements should be performed using the same device for each subject.
- Correct measurement requires a cuff that is appropriate to the size of the child's upper arm (US Department of Health and Human Services, 2005)
- Measurements should be taken in a quiet place. The child whose BP is to be measured should have avoided stimulant drugs or foods and have been sitting quietly for 5 minutes
- Tight-fitting clothing should be removed from the arm to be measured. The same arm should be used for all BP measurements
- During the measurement, the subject should be seated with feet flat on the floor, back supported and arm rested on a table so that the cuff is at the subject's heart level. If this is not possible, the same positioning of the subject should be maintained for BP measurement at each visit

Subject should remain still and should not talk during the measurement. BP data for each visit should be recorded in the respective eCRF.

7.4 Physical Examination

Physical examination should be performed as indicated in the Schedule of Events (see Appendix A and Appendix B). The following body systems are to be examined:

- Cardiovascular
- Lungs and chest, including respirations
- Head and neck
- Abdomen
- Musculoskeletal
- Skin
- Neurological

Any new clinically significant physical examination abnormality identified during the study should be reported as an AE.

7.5 ECG Assessment

The baseline 12-lead ECG may be performed on either Screening Visit 1 or Screening Visit 2; the end of study ECG will be performed at the Week 26 Visit or ET visit.

If the Investigator is concerned regarding any potassium value, a re-test of potassium level and/or ECG evaluation for electrophysiological consequences can be initiated by the Investigator at their discretion. An ECG is required when the local K^+ is > 6.0 mEq/L and must be followed by a Mandatory Safety Visit (See Section 6.5.1)

If a potassium-related ECG change is observed, the Investigator should apply the appropriate standard of care to stabilize the myocardium, which may include any or all of the following depending on the subject's clinical situation: intravenous calcium, intravenous insulin and glucose, inhaled beta₂ agonists. In all cases, the ECG should be repeated within 2 to 3 minutes following any of the above interventions, and the subject should be assessed for referral to an emergency care facility. Any subject with a potassium-related ECG change must be withdrawn early and once stable, should return for the ET Visit (see Section 6.4).

7.6 Patiromer Palatability

The palatability of patiromer will be evaluated in children ≥ 6 years of age when the initial dose is administered at the study site on Day 1 using a 5-point facial hedonic scale for taste and overall liking. Patiromer should be mixed with water on Day 1 for the palatability assessment. Parental or authorized legal representative response on a 5-point agreement/disagreement scale to a statement of the subject's (< 6 years of age) acceptance of patiromer will be assessed on Day 14.

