6.2.4 Day 14 Visit

Patiromer dose may be adjusted at the Week 2 (Day 14) Visit based on the potassium level measured locally according to the titration algorithm. A description of the patiromer dose titration algorithm is provided in Section 5.2.1.

The activities for Day 14 (\pm 3 day) are detailed below and in Appendix A:

- Subject's visit registration in IWRS
- Physical examination
- Body weight and height
- Vital Signs (resting heart rate and sitting BP)
- 12-Lead ECG (Only if local K⁺ is > 6.0 mEq)
- Potassium levels (measured locally and by central laboratory).
- Other central laboratory tests (see Appendix B):
 - Serum chemistry
 - Plasma parathyroid hormone
 - Serum fluoride
 - Urinalysis (not required for anuric subjects, see section 7.2)
 - Hematology (CBC)
- Patiromer dose titration (if needed), dispensation, reconciliation, accountability, compliance, and subject retraining (as applicable)
- Parent's or legally authorized representative's assessment of subject's (< 6 years of age) acceptance of patiromer
- Review of Subject Dosing Diary by Investigator and/or designee
- Assessment of AEs
- Assessment of concomitant medications
- Next visit scheduling

6.2.5 Week 3, Week 5, Week 7, Week 10, Week 14, Week 18, and Week 22 Visits

Patiromer dose may be adjusted at any scheduled visit based on the potassium level measured locally according to the titration algorithm. A description of the patiromer dose titration algorithm is provided in Section 5.2.1. Study visits at Week 3, Week 10 and Week 22 may be omitted under certain circumstances; refer to Section 3.2.3 for details. During the Long-Term Treatment Phase, up to 2 non-sequential study visits may be conducted remotely using the Sponsor approved Home Care vendor at certain investigational sites in certain countries; refer to Section 3.2.3 for details.

The activities for Week 3 (\pm 3 days) and Weeks 5, 7, 10, 14, 18, and 22 (\pm 7 days) are detailed below and in Appendix B:

- Subject's visit registration in IWRS
- Vital Signs (resting heart rate and sitting BP)
- 12-Lead ECG (Only if local K⁺ is > 6.0 mEq)

-
- Physical examination (Week 7 and Week 14 only); may be omitted for Home Care visit
- Body weight and height (Week 7 and Week 14 only); may be omitted for Home Care visit
- Potassium levels (measured locally and by central laboratory); the investigator will review local potassium results within 24 hours for any Home Care visit.

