Appendix A: Schedule of Events (Screening and Pharmacodynamic / Dose Finding Phase)

Study Activity	Phase	Screening			Pharmacodynamic / Dose Finding Phase			ET ^b	MSV ^c
	Scenario	Subject With Standard of Care Potassium	Subject Without Standard of Care Potassium		D3 ^a (± 1d)	D7 (± 3d)	D14 (± 3d)		
	Visit	SV1/D1	SV1	SV2/D1 (2 to 7 days after SV1)					
Informed Consent		X	X						
I/E Criteria		X		X					
Demographics		X	X						
Medical History		X	X ^d						
Physical Examination		X	X ^d				X	X	
Body Weight		X		X			X	X	
Height		X	X ^d				X	X	
Vital Signs (Resting Heart Rate and Sitting BP)		X	X	X	X	X	X	X	
12-Lead ECG		X	X ^d		X ^m	X ^m	X ^m	X	X ^l
Potassium		L&C ^e	L	L&C ^e	L&C	L&C	L&C	L&C	L&C
Chemistry ^f		L&C ^e		L&C ^e		C	C	C	
Hematology (CBC)		L&C ^e		L&C ^e			C	C	
Plasma Parathyroid hormone		C ^e		C ^e			C	C	
Serum Fluoride		C ^e		C ^e			C	C	
Urinalysis ^g		C ^e		C ^e			C	C	
Pregnancy Test ^h		L&C ^e		L&C ^e				L&C	
IWRS Entry		X	X	X	X	X	X	X	X
Patiromer Administration ⁱ		X ^e		X ^e	X ^j	X	X		X
Patiromer Palatability and Parental Assessment ^k		X ^e		X ^e			X		

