- ^k Palatability of patiromer will be evaluated in children ≥ 6 years of age when the initial dose is administered at the study site on Day 1 and parental or legal authorized representative response on the subject's (< 6 years of age) acceptance of patiromer will be assessed on Day 14 (see Section 7.6 for further details).
- ^l ECG at the Mandatory Safety Visit required only if the local potassium is >6.0 mEq/L at the current or prior visit (see Section 6.5.1)
- ^m ECG is only required if the local potassium is > 6.0 mEq/L

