7.10.5 Physical Examination

Abnormalities found in physical examinations will be listed at each scheduled visit for physical examination.

7.10.6 12-lead *Electrocardiogram (ECG)*

Number and percentage of subjects with normal/abnormal and clinically significant abnormal ECG findings will be summarized at each scheduled visit for 12-lead ECG.

A listing for 12-lead ECG will be provided.

7.10.7 *Pregnancy Test*

A listing of all pregnancy tests results will be provided.

7.11 *Palatability Assessments*

In children \geq 6 years old, patiromer palatability assessments (taste and overall liking) will be summarized using descriptive statistics. A 5-point scale for taste and overall liking includes dislike very much, dislike somewhat, neither like nor dislike, like somewhat, and like very much.

For children $<$ 6 years old, assessment of the subject's parental acceptance of patiromer will be summarized using descriptive statistics. A 5-point agreement/disagreement scale to a statement of the subject's ($<$ 6 years of age) acceptance of patiromer includes strongly disagree, somewhat disagree, neither agree nor disagree, somewhat agree, and strongly agree.

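### Under age 6, acceptance of patiromer is rated only at Day 14 and not at Early Termination, so a child who refuses and stops sooner goes unrated, and the summary would lean upward if such children occur

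*Protocol*

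**What the plan says.** For children under 6, Protocol 7.6 provides one parental rating on a five-point agreement scale: "acceptance of patiromer will be assessed on Day 14". Protocol 6.2.4 lists the parent's "assessment of subject's (< 6 years of age) acceptance of patiromer" among the Day 14 activities, with a window of ±3 days. In Appendix A the row "Patiromer Palatability and Parental Assessment" is marked at the two Day 1 columns and at Day 14. The ET cell is blank, and footnote k confines the under-6 item to Day 14. Appendix B has no such row.

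Under Protocol 6.3, subjects who stop patiromer early in either treatment phase "enter directly into the Follow-up Period". Protocol 6.4 adds: "Subjects who withdraw prematurely from the study before the Week 26 Visit will need to complete the ET Visit". Its activity list covers examination, laboratory tests, ECG, drug accountability and compliance, adverse events and concomitant medication, but not acceptance.

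SAP 5.3 repeats the Day 14 timing. SAP 7.11 says that "assessment of the subject's parental acceptance of patiromer will be summarized using descriptive statistics" and names the five response categories. It gives no denominator and no rule for a child without a rating. Protocol 9.7 leaves missing data to the SAP, but SAP Section 6 deals only with missing adverse event information and missing dates.

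**The concern.** Whether a child under 6 is rated depends on the child still being in the study at about two weeks. A child who will not take the suspension and is withdrawn before then would be expected to score low, and that child is the one not asked about. The selection therefore has a predictable direction for refusers.

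Children aged 6 and over do not have this problem in the same form. They are rated when the first dose is given on site, so their score does not depend on continuing treatment.

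At stake is how well the study describes whether children aged 2 to under 6 will take the product. By Protocol 1.3 this is the first study of patiromer in children, and the parental item is the only planned acceptance rating for the youngest group. A question that was not asked at ET cannot be reconstructed after database lock.

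**Working it through.** Neither document states an acceptance rate, a refusal rate or a sample size for this item, so there is no planned figure to reproduce. The check has four parts.

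**1. Which children can be rated**

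| Course of a child under 6 | Day 14 visit | ET visit | Rated? |
|---|---|---|---|
| Still in the study at the Day 14 visit (Day 11 at the earliest) | Yes, item listed (6.2.4) | n/a | Yes, even if few doses were taken |
| Stops before the Day 14 visit | No, goes to Follow-up (6.3) | Called for (6.4), item not listed | No |
| Stops after the Day 14 visit | Already attended | Called for, item not listed | Yes, at Day 14 |

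Only the second row loses the rating. Comparing 6.2.4 with 6.4, the other Day 14 clinical and laboratory assessments recur at ET: physical examination, weight, height, vital signs, potassium, chemistry, parathyroid hormone, fluoride, urinalysis and hematology. The acceptance item does not.

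**2. Size, by illustration**

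Inputs:
- N = 12 children dosed, the number per age group at the recommended dose (Protocol 9.3).
- d = children who refuse and stop unrated. Assumed 1 to 3.
- x = rated children whose parents agree. Assumed. The SAP defines no cut-off for agreement.

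Formulas: share among rated = x/(N − d). Share among all dosed, counting a refuser as not accepting = x/N. Difference = [x/(N − d)] × d/N.

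| d | x | Among rated (exact 95% CI) | Among all dosed (exact 95% CI) | Difference |
|---|---|---|---|---|
| 0 | any | x/12 | x/12 | 0 |
| 1 | 9 | 9/11 = 81.8% (48.2 to 97.7) | 9/12 = 75.0% (42.8 to 94.5) | 6.8 points |
| 2 | 8 | 8/10 = 80.0% (44.4 to 97.5) | 8/12 = 66.7% (34.9 to 90.1) | 13.3 points |
| 3 | 8 | 8/9 = 88.9% (51.8 to 99.7) | 8/12 = 66.7% (34.9 to 90.1) | 22.2 points |

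The Clopper-Pearson intervals are added here for scale. The SAP plans none for this item.

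**3. Chance that it arises at all**

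If each child has probability r of refusing and stopping before Day 14, the chance of at least one among n children is 1 − (1 − r)^n. With r assumed between 5% and 20%:
- n = 12: 1 − 0.95^12 = 46% to 1 − 0.80^12 = 93%.
- n = 18, the maximum per age group: 1 − 0.95^18 = 60% to 1 − 0.80^18 = 98%.

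**4. Effect of the denominator**

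SAP 4.2 points all analyses to the safety population, that is, every child dosed. On that reading, the two-refuser example shows agreement as 8/12 = 67%, with no inflation. However, the rated children who do not agree number 10 − 8 = 2, so non-agreement appears as 2/12 = 17% against (2 + 2)/12 = 33% if the refusers counted. The remaining 2/12 = 17% appears in no category unless the table has a row for unrated children.

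**The case against.** The strongest reply is that the documents do not show any overstatement. No refusal or early dropout rate is given, and with no early refuser the difference is zero. That is correct, so the point is conditional.

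A reader might also infer that SAP 7.11 will use only the ratings obtained. The SAP does not say so. It is silent on the denominator, and SAP 4.2 favours all dosed children. The 80% against 67% comparison therefore depends on an assumed denominator as well as assumed counts, and on a cut-off for agreement that the plan does not define.

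A third tempting reading is that every rated child has accepted the drug for 14 days. Protocol 4.3 lists poor compliance only as a possible reason for withdrawal. A child who takes few doses can still attend Day 14 and be scored low. Nor does every early stop bias the summary upward: a child withdrawn for an adverse event did not necessarily dislike the product, and the direction for that child is unknown.

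Refusal is not wholly invisible. Reasons for early termination, reasons for interruption or discontinuation, and compliance are all reported. These help, but refusal is not itself a listed withdrawal reason. It could be recorded as consent withdrawal, non-compliance or the investigator's decision, and representatives need not explain a withdrawal of consent. None of these sources feeds the acceptance table.

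Finally, Protocol 4.3 has the ET procedures done only where possible, so the remedy will miss some children. That limits the gain but does not remove it.

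**Conclusion.** The gap is confirmed: under age 6, acceptance is asked once, at Day 14, and not at ET, so a child who refuses and stops before that visit is unrated. If such children occur, the acceptance summary would be biased upward. The size cannot be determined from the documents. For one to three assumed refusers among 12, the illustrated difference is about 7 to 22 points if only rated children form the denominator. If all dosed children do, the share agreeing is not inflated, but the refusers would be missing from the unfavourable categories.

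The priority is minor. A reader might infer that the secondary objective on safety and tolerability is compromised. The documents do not support that: palatability and acceptance stand apart as an additional descriptive analysis (Protocol 9.6, SAP 5.3 and 7.11). The safety variables in Protocol 9.5 do not include the rating, and the dose assessment criteria in Protocol 8.6.1 do not name it.

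**What to change.** - **Protocol 6.4 and Appendix A:** add the same parental item to the ET visit for children under 6 who stop before Day 14, where the visit can be done.
- **SAP 7.11:** present the five categories over all dosed children under 6. Show Day 14 and ET ratings separately as well as combined, with a row for unrated children and their reasons for stopping.

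The SAP change is useful even without a protocol amendment, because it makes the number of unrated children visible.

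Cost: one extra question at a visit the protocol already calls for, a footnote in the schedule, and additional rows in one table. There are two downsides. ET ratings reflect a shorter exposure than Day 14 ratings, which is why they should also be shown apart, and the reported acceptance may be less favourable.
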